10.4 Phase I Design

A 3+3 design will be employed to determine the tolerability of lenalidomide maintenance at the dose of 10 mg daily in this setting. The dose will not be escalated, but in the event of 2 or more DLTs at 10 mg, the dose will be de-escalated to 5 mg.

Dose Level 1: Three evaluable patients will be treated at 10 mg lenalidomide.

If 2 or more of 3 evaluable patients have DLT, then the dose will be de-escalated to 5 mg.

If 0 or 1 of 3 evaluable patients has DLT, then 3 more evaluable patients will be treated at 10 mg daily.

If 0 or 1 of 6 evaluable patients has DLT, then 10 mg will be declared the appropriate dose for phase II part of the trial. 18 additional evaluable patients will then be enrolled in phase II.

If 2 or more of 6 evaluable patients have DLT, then the dose will be de-escalated to 5 mg daily.

Dose Level -1: Three evaluable patients will be treated at 5 mg lenalidomide.

If 2 or more of 3 evaluable patients have DLT, then the appropriate dose is not defined and the trial will be terminated.

If 0 or 1 of 3 evaluable patients has DLT, then 3 more evaluable patients will be treated at 5 mg daily.

If 0 or 1 of 6 evaluable patients has DLT, then 5 mg will be declared the appropriate dose.

18 additional evaluable patients will then be enrolled in phase II.

If 2 or more of 6 evaluable patients have DLT, then the appropriate dose is not defined and the trial will be terminated.

10.5 Rules for Early Termination for Dose Limiting Toxicity during Phase II

Bayesian probability calculations will be employed to define rules for early termination. The table below indicates termination rules after groups of 6 evaluable patients have been treated. We will assume prior information equivalent to that of 6 treated patients which is commonly required to establish safety in a standard 3+3 phase I design. We will assume a beta(1,5) prior, which is information equivalent to DLT observed in 1 of 6 treated patients. A DLT rate <33% is considered acceptable. If the number of patients with DLT is greater than or equal to the number in the table below then termination will be considered as it is likely that the DLT rate is >33%, as noted by the Bayesian posterior probabilities.

BAYESIAN TERMINATION RULE FOR DOSE LIMITING TOXICITY			
PATIENTS TREATED WITH LENALIDOMIDE	12	18	24
PATIENTS WHO EXPERIENCE DLT	7	9	11
POSTERIOR PROB [DLT RATE >33%]	0.84	0.80	0.78
ACTION	TERMINATE ENROLLMENT		

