10.1 Design

This is a single arm phase I/II trial of lenalidomide maintenance for patients with high risk relapsed/refractory lymphomas who underwent high dose chemotherapy and ASCT. At 28-100 days post-ASCT, eligible patients will begin lenalidomide maintenance. The trial will be conducted in two stages. Phase I will evaluate the safety of lenalidomide implemented after ASCT by a 3+3 cohort design. Once the safety of a specific dose after ASCT is established, additional patients will be enrolled in phase II to evaluate the progression-free survival. PFS is a relevant endpoint for lenalidomide maintenance since it is expected to delay progression of disease post-ASCT. A monitoring rule for unacceptable toxicity due to lenalidomide will be followed during phase II.

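### Once a dose has passed phase I, the phase II DLT rule seldom stops enrolment early, and its 24-patient look comes too late to do so

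*Combined protocol and SAP*

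**What the plan says.** Section 10.1 states: "A monitoring rule for unacceptable toxicity due to lenalidomide will be followed during phase II". Section 10.4 gives the condition for entering phase II: "If 0 or 1 of 6 evaluable patients has DLT, then 10 mg will be declared the appropriate dose" (the 5 mg level has the same criterion), and then "18 additional evaluable patients will then be enrolled in phase II".

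Section 10.5 gives the phase II rule. On timing: "The table below indicates termination rules after groups of 6 evaluable patients have been treated". On the prior: "We will assume a beta(1,5) prior, which is information equivalent to DLT observed in 1 of 6 treated patients". A DLT rate below 33% is called acceptable. The table gives bounds of 7 at 12, 9 at 18 and 11 at 24, with posterior probabilities of 0.84, 0.80 and 0.78 that the rate exceeds 33%. Its count row is labelled "PATIENTS TREATED WITH LENALIDOMIDE" and its action row "TERMINATE ENROLLMENT". The sentence above the table is softer: "If the number of patients with DLT is greater than or equal to the number in the table below then termination will be considered".

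Section 10.6 prints false positive and false negative rates for the PFS12 criterion. Section 10.5 prints none for the toxicity rule.

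**The concern.** Read alone, the table looks like a working safety rule: three looks, each with a posterior of about 0.8 that the DLT rate is too high. But patients reach phase II only after a favourable result in the first 6, and those 6 are part of every later count. The rule therefore starts from a low DLT count, and the later patients must do very badly to reach the bounds.

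Safety and the dose for further studies are the primary objective (Section 4.1.1). The phase II rule is the only numerical protection in the case where a dose that is too toxic passes phase I by chance. If it seldom acts before enrolment is complete, the reader should be told, and a cheap improvement should be considered.

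**Working it through.** **Inputs.** Phase I pass: at most 1 DLT in 6; then 18 more evaluable patients, so 6 + 18 = 24 (Sections 10.4, 10.7). Bounds 7/12, 9/18, 11/24; prior beta(1,5); limit 33% (Section 10.5). DLT window 28 days (Section 10.3). Accrual 8-10 patients a year (Section 10.8).

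**Reproducing the table.** With r DLTs in n patients, the posterior is P(Beta(1 + r, 5 + n − r) > 0.33). This gives 0.836 at 7/12, 0.803 at 9/18 and 0.780 at 11/24, which match the printed values. The match also shows that the counts are cumulative. If phase I served only as the prior and the data were 6 DLTs in 6 new patients, the posterior would be 0.963, not 0.84.

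**New DLTs needed after a phase I pass (counts at the selected dose).**

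| Look | Bound | After 1/6 | After 0/6 |
|---|---|---|---|
| 12 | 7 | 6 of 6 | 7 of 6: impossible |
| 18 | 9 | 8 of 12 | 9 of 12 |
| 24 | 11 | 10 of 18 | 11 of 18 |

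**Chance of stopping.** For a true rate p, the pass probability is (1 − p)^6 + 6p(1 − p)^5, which is 0.358/0.233/0.109/0.041 at 33/40/50/60%. Given a pass, the later groups are binomial, and all paths are enumerated exactly.

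Hand check at p = 0.50:
- The pass probability is 7/64, so phase I had 1 DLT with weight 6/7 and 0 with weight 1/7.
- 12-patient look: 6/7 × 0.5^6 = 0.0134.
- At or above 9 by 18: 6/7 × P(≥8 of 12) + 1/7 × P(≥9 of 12) = 6/7 × 0.194 + 1/7 × 0.073 = 0.1766.
- Add the paths that crossed at 12 but would be below 9 at 18: 0.0134 × P(≤1 of 6) = 0.0134 × 0.109 = 0.0015.
- Total before 24: 0.178.

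| Given a phase I pass, true DLT rate | 33% | 40% | 50% | 60% |
|---|---|---|---|---|
| Stop at 12 | 0.1% | 0.3% | 1.3% | 4.2% |
| Stop at 18 | 1.3% | 4.6% | 16.5% | 37.7% |
| **Stop before 24, as written** | **1.4%** | **5.0%** | **17.8%** | **41.9%** |
| Cross only at 24 | 2.4% | 7.9% | 21.9% | 31.0% |
| Stop before 24, same bounds, phase I condition ignored | 12% | 29% | 62% | 88% |
| Stop before 24, looks at 15 and 21 added | 2.8% | 9.3% | 30.0% | 60.6% |

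At 40% and 50%, 61% (7.9/12.9) and 55% (21.9/39.7) of all crossings fall at the last look. The fifth row shows that the phase I condition, not faulty arithmetic, explains most of the weakness.

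**Added looks under the plan's own prior and a cut-off of 0.78 (to two decimals).** At 15, 8 DLTs give 0.82 and 7 give 0.67, so the bound is 8. At 21, 10 give 0.79 and 9 give 0.66, so the bound is 10. False stops at a true 30%, given a pass, rise from 0.75% to 1.5%.

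**Effect over all trials.** Pass probability × gain in stopping: at 40%, 0.233 × (0.093 − 0.050) = 1.0 point; at 50%, 0.109 × (0.300 − 0.178) = 1.3 points; at 60%, 0.041 × (0.606 − 0.419) = 0.8 points.

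**The case against.** **The phase I stage is the real safeguard.** This stands. It excludes 1 − 0.233 = 77%, 1 − 0.109 = 89% and 1 − 0.041 = 96% of doses at true rates of 40/50/60%. The low stopping chances apply only to the minority that pass, which is why the gain over all trials is about one point. A true rate of 33% is the limit itself, so rare stopping there is not a failure.

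**The rule is not the only monitoring.** This also stands. Section 9.2 requires quarterly toxicity analyses. Section 6.3.2 sends related grade 3 or higher events to the DSMC within 10 days, lets the medical monitor recommend suspension or termination, and calls for IRB notice when toxicity exceeds expectation. A reader might infer that phase II patients are unprotected; the documents do not support that. What these reviews lack is a numerical criterion.

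**The prior is stated and the posteriors are right.** Correct. A reader might infer that adding beta(1,5) to the phase I data is a double-counting error. It is not: a stated prior updated with all data is a permitted choice. It makes the rule more tolerant, raising each bound by about one DLT compared with a weak prior, but it is a contributing cause, not a mistake. A reader might likewise infer that the bounds must be lowered. Bounds of 6/12 and 8/18 would stop 14.5/36.9/65.0% at 40/50/60% given a pass, but with 3.4% false stops at a true 30%. That is a trade-off for the sponsor to weigh.

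**The 24-patient look might still act.** This is partly right. The row label does not say evaluable or selected dose. If 6 patients at a de-escalated 10 mg level were also counted, the total would be 6 + 6 + 18 = 30 and the 24th would fall during accrual; treated but non-evaluable patients would have a similar effect. The text above the table does refer to evaluable patients, which supports the reading used here where there is no de-escalation. The ambiguity itself needs resolving.

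**Conclusion.** The point holds as a cheap improvement of minor to moderate weight. Given a phase I pass, the rule stops enrolment before 24 in 5.0% of trials at a true DLT rate of 40%, 17.8% at 50% and 41.9% at 60%. One of the two permitted phase I results makes the first bound unreachable, and the last look has no planned evaluable accrual left to stop. Enrolling about 28 does not change this, because the extra patients replace those who never receive lenalidomide.

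These figures assume independent patients with a constant DLT rate, complete DLT data at each look, counts of evaluable patients at the selected dose including phase I, and stopping whenever a bound is met. If termination is only considered, actual stopping may be rarer.

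On wording, a rule that calls for consideration can still be followed, so Section 10.1 is not in clear conflict with Section 10.5. The mismatch lies within Section 10.5, between considering termination and the table's instruction.

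**What to change.** In Section 10.5:

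1. Keep the beta(1,5) prior, the cut-off of about 0.78 and the bounds 7/12 and 9/18. Add looks at 15 (bound 8, posterior 0.82) and 21 (bound 10, posterior 0.79).
2. Relabel the 24-patient column as a final safety assessment that informs the dose conclusion.
3. State that the counts are evaluable patients at the selected dose, including those from phase I.
4. Reconcile "If the number of patients with DLT is greater than or equal to the number in the table below then termination will be considered" with "TERMINATE ENROLLMENT", so that it is clear what meeting a bound triggers.
5. Print the chance of stopping by true DLT rate, conditional on the phase I pass.

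The cost is two table columns, a few sentences, two more looks and the rise in false stops at a true 30% from 0.75% to 1.5% given a pass. The looks are feasible: at 8-10 patients a year, entries average 365/10 = 37 to 365/8 = 46 days apart, longer than the 28-day DLT window. Detection at a true 40% remains modest (9.3%), and the printed operating characteristics should let the reader see that. Items 2 to 5 are worth making even if the sponsor keeps the present looks.

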10.6 Plans for Data Analysis

All observed toxicities will be graded and tabled. The toxicities may be stratified as either related to lenalidomide or other medications (i.e. high dose chemotherapy and ASCT). Progression-free survival and overall survival will be estimated by the method of Kaplan and Meier. A minimum of 12 months of observation time is required on all patients (or less if patient has failed), in order to estimate PFS12. The PFS12 rate and 95% confidence interval will be computed. In addition to the observed rate and 95% CI, evidence for success of lenalidomide will be assumed if >4 of 24 evaluable patients are alive and progression-free at 12 months, based on operating characteristics defined by binomial probabilities. The probability of observing >4 patients alive and progression-free in 24 patients when true rate is 10%, is 0.09 (false positive rate). The probability of observing ≤4 patients alive and progression-free when true rate is 30%, is 0.11 (false negative rate).

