5.3.5 Radiographic Evaluations

Subjects will undergo radiographic evaluations to assess disease status at the timepoints listed below. Timing of radiographic evaluations may be altered based on clinical indication or the discretion of the treating physician.

- PET/CT after at least 2 cycles of salvage chemotherapy, but prior ASCT (using separate PET scan and dedicated CT scan performed within one week is acceptable)
- Imaging (PET/CT or CT scan) after ASCT, but prior Cycle 1 of lenalidomide therapy
- Imaging (PET/CT or CT scan) every 3 cycles during the first year of lenalidomide maintenance therapy (near end of Cycles 3, 6, 9, 12)
- Imaging (PET/CT or CT scan) every 4 cycles during second year of lenalidomide maintenance therapy (near end of Cycles 16, 20, 24)

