5.7 Discontinuation of Study Treatment

Study treatment will continue until the completion of 24 cycles of lenalidomide maintenance therapy, or the occurrence of any of the following events:

- Disease progression (See Appendix D)
- Adverse event(s) that, in the judgment of the Investigator, may cause severe or permanent harm or which rule out continuation of the treatment regimen.
- Discontinuation or interruption in lenalidomide therapy for ≥ 28 consecutive days.
- Withdrawal of consent
- Lost to follow up
- Death
- Pregnancy or a positive pregnancy test

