10.3 Endpoints

Dose-limiting toxicity (DLT) is defined as any grade 3 toxicity or higher that occurs during the first 28 days of therapy and is possibly, probably or definitely related to lenalidomide maintenance. Because certain levels of toxicity are considered acceptable in lymphoma therapy, the definition of DLT is limited to the following:

-Any grade 3 or higher non-hematologic toxicity possibly, probably or definitely related to lenalidomide.

-Grade 4 hematologic toxicity not attributable to progressive disease and that does not decrease to a grade 3 or less within 7 days of drug cessation.

-Lymphopenia of any grade and anemia of any grade are not considered a DLT.

-Nausea and vomiting are not considered DLTs unless they cannot be controlled with standard antiemetic therapy.

-Diarrhea is not considered a DLT unless it cannot be controlled with standard anti-diarrheal therapy.

-Nausea, vomiting, heartburn, anorexia, diarrhea, or constipation that improved to grade 1 or better within 2 days with the addition of symptom directed treatment will not be considered a DLT.

NCI Common toxicity criteria (CTC Version 4.0) grades will be employed. Toxicity unrelated to lenalidomide (i.e. clearly related to ASCT) will be scored separately.

Progression-free survival (PFS) is defined from date of ASCT (day 0) to first documented progression of disease, death due to any cause or last patient contact. Progression-free survival rate at 12 months (PFS12) is also of interest and is defined as the percentage of patients that are alive and progression-free at 12 months. Overall survival (OS) is defined as days from date of ASCT to death due to any cause or last patient contact.

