Patients are enrolled 28 to 100 days after ASCT (day 0). Patients who complete one full cycle of lenalidomide maintenance or who experience DLT during the first cycle will be considered evaluable for DLT determination. Patients who withdraw from the study prior to initiation of lenalidomide maintenance, or who initiate and discontinue lenalidomide maintenance before completing one full cycle and do not experience DLT, remain in the study population and are followed for PFS and OS but do not contribute to the determination of DLT. These patients will be included in the estimation of PFS and OS, according to an intent-to-treat analysis plan. A secondary analysis of PFS and OS will include only patients who complete at least one full cycle of lenalidomide or who experience DLT at any point during cycle 1 (“evaluable population”). Patients who did not progress will be censored at the time of last contact. Evaluable patients contribute to determination of DLT, PFS and OS. Evaluable patient outcomes will be compared to historical rates for PFS12.

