10.7 Sample Size

Twenty-four evaluable patients will be enrolled. If the rate of enrolled patients who underwent ASCT and do not receive lenalidomide is about 15% then at least 28 patients may need to be enrolled. Regimens of high dose chemotherapy and ASCT for high risk (PET positive) lymphomas have historically produced a PFS12 of <10%. Single agent lenalidomide in relapsed/refractory lymphomas has been shown to produce a PFS12 of approximately 30%. The use of lenalidomide after high dose chemotherapy and ASCT will be considered worthy of further development if the PFS12 is 30% and will be considered not worthy of further development if the PFS12 is 10%. A total of 24 evaluable patients will provide 89% power for an exact test for a single proportion, with null rate of no interest (π_0) of 10%, alternative rate of interest (π_A) of 30%, at one-sided type I error (α) = 10%. A one-sided test is appropriate for early phase trials seeking to detect an improvement over historical rates.

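### The PFS12 success rule and the historical comparison use only evaluable patients, which drops those who progress, or die without a DLT, before completing cycle 1; that exclusion can only raise the rate

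*Combined protocol and SAP*

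**What the plan says.** All references are to the combined protocol and SAP.

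- **PFS event (10.3).** PFS runs from the date of ASCT to "first documented progression of disease, death due to any cause or last patient contact". PFS12 is defined there as a percentage of patients, with no restriction to evaluable ones.
- **Evaluable (10.3).** A patient is evaluable after completing one full cycle (28 days, section 5.1) or after a DLT in cycle 1. Of those who stop earlier without a DLT, or never start, the section says: "These patients will be included in the estimation of PFS and OS, according to an intent-to-treat analysis plan".
- **Status of the evaluable analysis (10.3).** "A secondary analysis of PFS and OS will include only patients who complete at least one full cycle of lenalidomide", or who have a DLT in cycle 1. The same section then says: "Evaluable patient outcomes will be compared to historical rates for PFS12".
- **Success rule (10.6).** "evidence for success of lenalidomide will be assumed if >4 of 24 evaluable patients are alive and progression-free at 12 months". The stated error rates are 0.09 (false positive at 10%) and 0.11 (false negative at 30%).
- **Sample size (10.7).** "Twenty-four evaluable patients will be enrolled". Power is given as 89% at a one-sided alpha of 10%. The 15% allowance covers only enrolled patients who never receive lenalidomide.
- **Stopping treatment (5.7).** Disease progression and death both end study treatment.

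**The concern.** Read together, these sections make a patient who progresses, or dies without a DLT, before completing cycle 1 a failure for PFS12 but not a member of the set on which PFS12 is judged. Membership of that set therefore depends partly on the outcome being measured.

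The plan also conflicts with itself. It adopts intent-to-treat for PFS and labels the evaluable analysis secondary, then rests the success rule, the historical comparison and the sample size on the evaluable set. The intent-to-treat estimate and the rule could point in different directions, and the plan does not say which prevails.

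The stake is the claim that lenalidomide shows evidence of success. The Kaplan-Meier estimate in all patients is not affected, and PFS is a secondary endpoint, so the harm is confined to the decision rule and the historical comparison. Section 10.7 does, however, size the trial on that rule.

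**Working it through.** **Inputs from the documents.** n = 24 evaluable; success at 5 or more (10.6); null rate 10%, alternative 30%, nominal one-sided alpha 10% (10.7); observed historical PFS12 in PET-positive patients 7% (3.1).

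**Step 1: the plan's own figures.** With X binomial on n = 24:
- P(X ≥ 5 | 0.10) = 0.0851, stated as 0.09.
- P(X ≥ 5 | 0.30) = 0.8889, stated as 89%. The false-negative rate is 1 − 0.8889 = 0.1111, stated as 0.11.

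The figures reproduce. They describe all starters only if no cycle-1 failure is removed.

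**Step 2: direction.** Each omitted patient is a certain PFS12 failure. Leaving one out keeps the numerator and shrinks the denominator. With 5 successes, 5/24 = 20.8% would be 5/25 = 20.0% with one omitted failure restored and 5/26 = 19.2% with two.

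**Step 3: size.** Let q be the share of starters omitted in this way, with the set then filled to 24 evaluable. Filling is inferred from the fixed target; no replacement rule is written. If the true PFS12 among starters is p, the rate among evaluable patients is p/(1 − q). The documents give no value for q, so a range is assumed. At p = 0.10:

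| q (assumed) | 0.10/(1 − q) | P(X ≥ 5 of 24) |
|---|---|---|
| 0 | 0.1000 | 0.0851 |
| 2% | 0.1020 | 0.0910 |
| 4% | 0.1042 | 0.0975 |
| 5% | 0.1053 | 0.1009 |
| 10% | 0.1111 | 0.1203 |
| 15% | 0.1176 | 0.1439 |

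The probability reaches 0.10 at q = 0.0473. That is 24 × 0.0473/(1 − 0.0473) = 1.19 omitted patients per 24 evaluable.

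**Step 4: if the true rate is 7%.** P(X ≥ 5) is 0.0233 at q = 0. At q = 15% the rate is 0.07/0.85 = 0.0824 and P(X ≥ 5) is 0.0429. Both are below 0.10.

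**Step 5: a rule on all enrolled patients, taking n = 28.**
- Keeping 5 or more of 28 gives alpha 0.142, so the cut-off would have to move.
- 6 or more of 28 gives alpha 0.0550 and power 0.8872 at 30%.
- If the 15% untreated have a PFS12 of 10%, the overall rate is 0.85 × 0.30 + 0.15 × 0.10 = 0.27 and power is 0.8075.
- If none of them is progression-free at 12 months, the rate is 0.85 × 0.30 = 0.255 and power is 0.7554.

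**The case against.** The strongest reply is that the effect is probably small and partly covered already.

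- **An intent-to-treat estimate is planned.** Section 10.6 presents the success rule as an addition to the PFS12 rate and its 95% CI, so a reader would see both. This stands. It limits the harm but does not change which set governs the rule.
- **Few patients are likely to be lost this way.** Progression on the post-ASCT scan is an exclusion (5.2.2), on-treatment scans in the first year fall "near end of Cycles 3, 6, 9, 12" (5.3.5), and patients with a cycle-1 DLT stay in. What remains is progression found clinically or on an unscheduled scan, or death without a DLT, within 28 days. One such patient among 25 starters (q = 4%) still gives 0.0975. This stands, and it makes the low end of the range more likely.
- **The 10% null is above the observed 7%.** At 7% the rule stays within 0.10 throughout the range. This also stands, but section 10.7 states its error rate at 10%.
- **The inflation needs replacement.** With exactly 24 starters and no refilling, the chance of 5 or more successes stays at 0.085. True, but a target of 24 evaluable patients, from an enrolment of at least 28, implies refilling.
- **The net direction of the whole evaluability rule is not established.** It also drops patients who never start, or who stop in cycle 1 for other reasons, and some of these may be progression-free at 12 months. This is correct. The upward direction is claimed only for the patients named here.

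**Conclusion.** The concern holds and should be fixed. The success rule and the historical comparison use a set that the plan itself calls secondary and that leaves out certain PFS failures. This exclusion can bias the rate only upward.

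The size rests on an assumed loss rate and on refilling to 24. For losses of 2% to 15% of starters, the false-positive chance at a true 10% goes from 0.085 to between 0.091 and 0.144, with the lower figures more likely. The margin is thin: about 1.2 omitted patients per 24 evaluable take it past the nominal 0.10. The effect of entry at days 28–100 after ASCT is a separate issue and is not counted in these figures.

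**What to change.** In sections 10.3 and 10.6:

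1. Apply the success rule and the historical comparison to the first 24 patients who start lenalidomide at the dose carried into phase II. Count any progression or death in cycle 1 as failure. The cut-off of 5 or more of 24 then keeps alpha 0.085 and power 0.889, given known 12-month status for all 24.
2. State how starters with unknown 12-month status are counted. As an illustration, if 5% or 10% were unknown independently of outcome and counted as failures, the 30% rate becomes 0.95 × 0.30 = 0.285 or 0.90 × 0.30 = 0.27, and power is 0.856 or 0.817.
3. Keep the evaluable set for DLT and as a sensitivity analysis for PFS12.
4. Report PFS12 with its 95% CI in all enrolled patients.

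If the rule is instead applied to all enrolled patients, fix n in advance (section 10.7 gives only a minimum of 28) and reset the cut-off. The figures for 6 or more of 28 are in the working.

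The cost is wording only. No extra patients or visits are needed, because all starters are already followed for PFS. The PFS12 used by the rule may come out slightly less favourable.
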